Each treatment arm will be stratified according to 1) the response to second-line induction therapy (PR, nPR, CRi or CR versus MRD-negative CR); 2) age ( $\leq 70$  versus  $> 70$  years); and 3) presence of at least one of the following poor prognostic factors: 11q deletion, 17p deletion, unmutated IgVH or  $\beta 2M > 4.0$  mg/L (Yes versus No versus Unknown).

The subjects randomized to the lenalidomide treatment arm will continue to receive lenalidomide study drug up to PD. Subjects who discontinue therapy, will enter the survival follow-up phase of the study. Subjects will be assessed for subsequent CLL therapies, second primary malignancies, recovery from serious adverse events (SAEs), and any new SAEs or AEs related to study procedures or prior maintenance therapy.

Subjects randomized to the placebo arm and currently on treatment at the time of Amendment #10 and patients who previously discontinued from the study drug and will be followed every 24 weeks for survival, subsequent CLL therapies, response to next therapy and progression

following next therapy, and second primary malignancies. Subjects will be followed until all subjects in the study have been followed for at least 5 years from the last randomization, October 2020 (or have died/become lost to follow-up before 5 years).

Amendment #11:

Subjects currently on lenalidomide treatment will discontinue lenalidomide treatment immediately and complete the Treatment Discontinuation assessment. The subjects will then transition to the survival follow-up period.

Screening

Subjects will sign informed consent prior to undergoing any study-related procedures. Screening assessments for protocol eligibility will be performed within 28 days prior to randomization as outlined in [Table 2: Schedule of Assessments](#). Subjects who develop PD during screening will not be eligible to enroll into this study.

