**Table 2 Schedule of Assessments (Continued)**

Procedure a	Maintenance Therapy				After Treatment Discontinuation
	Screening $\leq$ 28 days prior to Day 1	Study Day 1	Every 28 days (4 weeks)	Tx discontinuation	Survival Follow-up: b Every 24 weeks (+/- 7 days)
Tumor lysis monitoring and prophylaxis (allopurinol administration) and tumor flare reaction monitoring n	X	X	X	--	--
Study drug administration o	--	X	X	--	--
Adverse events b,p	X	X	X	X	--
Assessment of Second Primary Malignancies q	X	X	X	X	X
████████████████████	█	█	█	█	█
Assessment of response f	--	--	X	X	--
Survival b	--	--	--	--	X

ALC = absolute lymphocyte count; ANC = absolute neutrophil count; ALT = alanine aminotransferase; AST = aspartate aminotransferase; CLL = chronic lymphocytic leukemia; CR = complete response; CRi = complete response with incomplete bone marrow recovery; CRF = case report form; CT = computed tomography; DAT = direct antiglobulin test; ECG = electrocardiogram; ECOG = Eastern Cooperative Oncology Group; FISH = fluorescence in-situ hybridization; HCT = hematocrit; HGB = hemoglobin; ICF = informed consent form; NK = natural killer; nPR = nodular partial response; PD = progressive disease; PR = partial response; SAE = serious adverse event; WBC = white blood cell; ZAP-70 = Zeta-chain Associated Protein kinase 70

a All study procedures should be performed within  $\pm$  3 days of the scheduled visit unless otherwise stated.

b Subjects who discontinued from the study drug will be followed for survival, subsequent CLL therapies, response to next therapy and progression following next therapy, and second primary malignancies at each of these visits. Subjects will be followed until all subjects in the study have been followed for at least 5 years from last subject randomized, October 2020, (or have died/become lost to follow-up before 5 years).

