k ECG will be performed at baseline and at treatment discontinuation and interpreted locally.

l [REDACTED]

n Tumor lysis prophylaxis, consisting of oral hydration and allopurinol 300 mg/day, will be administered for **3 days prior to starting treatment** and for at least the first cycle of each dose level. At the investigator’s discretion, allopurinol prophylaxis may be omitted for subjects entering the study with a CR; however subjects must be advised of the need for adequate hydration.

[figure not shown]
o Study drug to be dispensed in 28-day cycles. Subjects should be instructed to return the bottle every 28 days.

p Adverse events that lead to study discontinuation should be followed until resolution or stabilization. Serious adverse events should be monitored for 30 days after treatment discontinuation. All SAEs should be followed until resolution or stabilization. Any SAE deemed by the investigator to be related to study drug should be reported and followed until resolution.

q Second primary malignancies will be monitored as events of interest and must be reported as serious adverse events. This includes any second primary malignancy, regardless of causal relationship to study drug, occurring at any time for the duration of the study, from the time of signing the informed consent up to and including the survival follow-up period. Subjects will be followed until all subjects in the study have been followed for at least 5 years from randomization (or died/become lost to follow-up before 5 years). Events of second primary malignancy are to be reported using the SAE report form and must be considered an “Important Medical Event” even if no other serious criteria apply; these events must also be documented in the appropriate page(s) of the CRF and subject’s source documents. Documentation on the diagnosis of the second primary malignancy must be provided at the time of reporting as a serious adverse event (eg, any confirmatory histology or cytology results, X-rays, CT scans, etc.).

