**After Study Discontinuation:**

Upon discontinuation of study drug, subjects will be followed every 24 weeks for survival, information on other CLL treatments, response to next therapy and progression following next therapy, and second primary malignancies (reported as SAEs). Subjects will be followed until all subjects in the study have been followed for at least 5 years from the last randomization, October 2020 (or have died/become lost to follow-up before 5 years).

FCBP with regular menstrual cycles discontinued from treatment must have a pregnancy test on day 28 after the treatment discontinuation visit. FCBP with irregular cycles discontinued from treatment must have a pregnancy test on days 14 and 28 after the treatment discontinuation visit.

SAEs will continue to be collected for the first 30 days after the treatment discontinuation visit. Following 30 days post the treatment discontinuation visit, only SAEs related to maintenance therapy will be collected for the study duration. Second primary malignancies must be reported as SAEs. This includes any second primary malignancy, regardless of causal relationship to study medication, occurring at any time for the duration of the study, from the time of signing the informed consent up to and including progression free follow-up and survival follow-up.

[REDACTED]

[REDACTED]

[REDACTED]

[REDACTED]

[REDACTED]

[REDACTED]

[REDACTED]

[REDACTED]

[REDACTED]

[REDACTED]

[REDACTED]

[REDACTED]

[REDACTED]

[REDACTED]

[REDACTED]

[REDACTED]

[REDACTED]

[REDACTED]

[REDACTED]

[REDACTED]

[REDACTED]

[REDACTED]

[REDACTED]

[REDACTED]

[REDACTED]

[REDACTED]

[REDACTED]

[REDACTED]

[REDACTED]

[REDACTED]

[REDACTED]

[REDACTED]

[REDACTED]

[REDACTED]

[REDACTED]

[REDACTED]

[REDACTED]

[REDACTED]

[REDACTED]

[REDACTED]

[REDACTED]

[REDACTED]

[REDACTED]

[REDACTED]

[REDACTED]

[REDACTED]

[REDACTED]

[REDACTED]

[REDACTED]

[REDACTED]

[REDACTED]

[REDACTED]

[REDACTED]

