### 16.7. Safety Evaluation

All subjects who receive at least one dose of study medication will be included in the safety analyses.

Adverse events (AE) will be classified using the Medical Dictionary for Regulatory Activities (MedDRA) classification system. The severity of the toxicities will be graded according to the NCI CTCAE version 3.0 whenever possible.

The adverse event of infection will also be analyzed according to the grading system as recommended by the IWCLL guidelines for the diagnosis and treatment of CLL [REDACTED] ([Appendix 22.4](#)).

AE frequency will be tabulated by body system, MedDRA preferred term for each treatment regimen during the Treatment Phase. In the by-subject analysis, a subject having the same event more than once will be counted only once. AEs will be summarized by worst NCI CTCAE version 3.0 grade. AEs leading to death or to discontinuation from treatment, events classified as NCI CTCAE version 3.0 Grade 3 or higher, study-drug-related events, serious adverse events (SAEs), and events of interest (including second primary malignancies) will be summarized separately.

Laboratory data will be graded according to NCI CTCAE version 3.0 severity grade. Cross tabulations will be provided to summarize frequencies of abnormalities.

For vital sign and body weight data, means, medians, standard deviations, minimum, and maximum values will be provided.

Graphical displays will be provided where useful to assist in the interpretation of results.

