## 22. APPENDICES

### 22.1. Adverse Event

An adverse event (AE) is any noxious, unintended, or untoward medical occurrence occurring at any dose that may appear or worsen in a subject during the course of a study. It may be a new intercurrent illness, a worsening concomitant illness, an injury, or any concomitant impairment of the subject's health, including laboratory test values (as specified by the criteria below), regardless of etiology. Any medical condition that was present prior to study treatment and that remains unchanged or improved should not be recorded as an AE. If there is a worsening of that medical condition, this should be considered an AE. A diagnosis or syndrome should be recorded on the AE page of the electronic Case Report Form rather than the individual signs or symptoms of the diagnosis or syndrome.

All AEs will be recorded by the Investigator(s) from the time of signing of informed consent form to 30 days after the treatment discontinuation visit. All AEs that lead to study discontinuation should be followed until resolution or stabilization. AEs will be recorded on the AE page of the CRF and in the subject's source documents.

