### **Immediate reporting of serious adverse events**

Any AE that meets the criterion for a SAE requires the completion of a SAE Report Form in addition to being recorded on the AE pages of the CRF. The Investigator(s) is required to ensure that the data on these forms is accurate and consistent. This applies to all SAEs, regardless of relationship to study drug, that occur during the study, those made known to the Investigator(s) within 30 days after a subject's treatment discontinuation visit, and those made known to the investigator(s) at anytime that are suspected of being related to study drug.

Second primary malignancies will be monitored as events of interest and must be reported as serious adverse events. This includes any second primary malignancy, regardless of causal relationship to study medication, occurring at any time for the duration of the study, from the time of signing the ICF up to and including any follow-up, observation and/or survival follow-up period. In this study, subjects will be followed until all subjects in the study have been followed for at least 5 years from the last randomization, October 2020 (or have died/become lost to follow-up before 5 years). Events of second primary malignancy are to be reported using the SAE report form and must be considered an "Important Medical Event" even if no other serious criteria apply; these events must also be documented in the appropriate page(s) of the CRF and subject's source documents. Documentation of the diagnosis of the second primary malignancy must be provided at the time of reporting as a serious adverse event (eg, any confirmatory histology or cytology results).

Grade 4 hematologic abnormalities are expected in patients with CLL, and are also observed in patients receiving lenalidomide. The investigator will use their judgement to classify the seriousness of laboratory abnormality events. Laboratory values will be captured within the study database and will be reviewed on an ongoing basis by the sponsor and (provided that it is determined that any observed individual abnormalities or patterns of abnormalities do not warrant prompt communication to Health Authorities) will be reported to Health Authorities in periodic safety reports.

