12.1. Adverse Events

Adverse events (AE) will be classified using the Medical Dictionary for Regulatory Activities (MedDRA) classification system. The severity of the toxicities will be graded according to the NCI CTCAE version 3.0 whenever possible.

The adverse event of infection will also be analyzed according to the grading system as recommended by the IWCLL guidelines for the diagnosis and treatment of CLL [REDACTED] (Appendix 22.4).

Treatment emergent adverse events (AEs) will be summarized by treatment group and overall. A treatment emergent adverse event is defined as any AE occurring or worsening on or after the first treatment of any study drug, and within 30 days after the last dose of the last study drug received. Adverse events will be summarized by treatment arm and overall. Adverse events are documented on the CRF together with their severity, according to the NCI CTCAE version 3.0 or higher, also referred to as NCI toxicity grading. For the categorization of the adverse events, the Medical Dictionary for Regulatory Activities (MedDRA[®]) dictionary (version 16.0) will be used.

AE frequency will be tabulated by body system, MedDRA preferred term for each treatment regimen during the Treatment Phase as well as for the Follow-up Phase when appropriate. In the by-subject analysis, a subject having the same event more than once will be counted only once. AEs will be summarized by worst NCI CTCAE version 3.0 grade. In the case that the AEs or event frequencies are judged to be clinically important, an exact test may be used to analyze the difference between the treatment groups. In addition, AEs of special interest (Event of Interest),

including second primary malignancies (SPM), will be defined and summarized by treatment arm.

AEs leading to death or to discontinuation from treatment, events classified as NCI CTCAE version 3.0 Grade 3 or higher, study-drug-related events, serious adverse events (SAEs) and events of interest (including second primary malignancies) will be summarized separately.

Individual AE listings by subject will be provided.

[REDACTED]

Adverse events (AE) will be classified using the Medical Dictionary for Regulatory Activities (MedDRA) classification system. The severity of the toxicities will be graded according to the NCI CTCAE version 3.0 whenever possible.

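### In the visible text, adverse events are tabulated by arm only as crude once-per-subject incidence, although most collection closes about 30 days after treatment and time on treatment is planned to differ by arm

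*Protocol*

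**What the plan says.** **How AEs are summarized.** Protocol 16.7: "AE frequency will be tabulated by body system, MedDRA preferred term for each treatment regimen during the Treatment Phase". A subject with repeated occurrences of an event counts once. The Synopsis safety paragraph speaks of subject incidence and gives no person-time denominator. SAP 12.1 follows the same rule, adds Follow-up Phase tables where appropriate, and permits an exact test between arms when events are judged clinically important.

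**When collection stops.** Protocol 22.1: "All AEs will be recorded by the Investigator(s) from the time of signing of informed consent form to 30 days after the treatment discontinuation visit". SAP 12.1 defines treatment-emergent events as those on or after first dose "and within 30 days after the last dose of the last study drug received".

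**What is collected for longer.**
- Related SAEs. Protocol 8.1, After Study Discontinuation: "Following 30 days post the treatment discontinuation visit, only SAEs related to maintenance therapy will be collected for the study duration". Protocol 22.1 likewise takes in "those made known to the investigator(s) at anytime that are suspected of being related to study drug".
- Related events in follow-up. The Synopsis (Study Design) lists "any new SAEs or AEs related to study procedures or prior maintenance therapy".
- Second primary malignancies (SPMs). Protocol Table 2, footnote q: "This includes any second primary malignancy, regardless of causal relationship to study drug, occurring at any time for the duration of the study". Footnote b sets the end of follow-up: "Subjects will be followed until all subjects in the study have been followed for at least 5 years from last subject randomized, October 2020".

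**How long treatment lasts.** Both arms were to be treated to progression (Synopsis, Randomization). SAP 6.1 plans median PFS of 20 months on placebo and 32.3 months on lenalidomide. At Amendment 10 placebo treatment ended, while lenalidomide could continue at the investigator's discretion (Synopsis, Study Duration; Protocol 12.3). Amendment 11 then ended lenalidomide.

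**The concern.** Safety against placebo is the trial's secondary objective. A once-per-subject percentage depends on the event rate and on how long the subject is watched. If lenalidomide delays progression as planned, its subjects are watched longer and will show more events even where the underlying rate is the same. If toxicity stops lenalidomide early (Protocol 10.6 lists AEs as a reason for discontinuation), its subjects are watched for less time and real harm can be hidden. The crude percentage alone does not separate the two. After Amendment 10 there is a further asymmetry, because on-treatment time can accrue in one arm only. Type I error and power for the efficacy endpoints are not involved.

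**Working it through.** **Inputs from the documents.** PFS medians 20 and 32.3 months, exponential, and 160 subjects per arm (SAP 6.1); first-step analysis at 160 PFS events (SAP 11). The two medians agree with the design hazard ratio: 20/0.62 = 32.3.

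**Assumptions, because the documents give no figure.** The same true AE rate r = 0.10 per patient-year in both arms; uniform accrual over A = 2, 3, 4 or 5 years; progression or death the only reason to stop, unless stated otherwise.

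**Step 1, hazard of leaving treatment per year.**
- Placebo: h = ln 2/(20/12) = 0.416.
- Lenalidomide: h = ln 2/(32.3/12) = 0.258.

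**Step 2, date of the cut.** The expected number of PFS events reaches 160 at 38, 45, 52 and 59 months for A = 2, 3, 4 and 5. (At A = 5 this falls just before accrual would end.) Mean time on treatment by then is 1.38-1.40 years on placebo and 1.63-1.69 years on lenalidomide.

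**Step 3, crude incidence.** For potential follow-up c, the probability of at least one event on treatment is r/(r+h) × [1 − exp(−(r+h)c)], averaged over c.
- Placebo 12.4-12.7%, lenalidomide 14.7-14.9%.
- Ratios for A = 2, 3, 4, 5: 1.160, 1.169, 1.183, 1.200.
- With r = 0.02 the ratio is 1.166-1.215; with r = 0.50 it is 1.129-1.144.
- Adding the 30-day tail (simulation) gives 1.14-1.19.

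**Step 4, the same data per patient-year.** Time at risk for a first event is [1 − exp(−(r+h)c)]/(r+h), so incidence divided by time at risk equals r in each arm and the rate ratio is 1.00. Simulation with the tail gives 0.996-1.003. A common cut does not do this alone: moved 0 to 1 year later, it still leaves a crude ratio of 1.16-1.24.

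**Step 5, toxicity stopping on lenalidomide only.** The documents give no rate, so a range is shown.

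| Added stopping hazard per year | Share stopped by the cut | Crude ratio, equal true rates |
|---|---|---|
| 0.05 | 8% | 1.105-1.130 |
| 0.10 | 15% | 1.055-1.067 |
| 0.158 | 22% | 1.00 |
| 0.30 | 35-37% | 0.865-0.884 |

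**Step 6, a data cut after Amendment 10.** If the placebo window closes 0 to 1 year after the 160-event date and lenalidomide is counted 1 to 3 years longer, the crude ratio is 1.40-1.89 without toxicity stopping and 0.92-1.18 with about 36% stopping. These gaps are assumed.

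**Step 7, why SPMs must not share that cut.** With the planned OS medians of 3 and 4.84 years (SAP 6.1), and Amendment 10 assumed 0 to 1 year after the 160-event date, cutting there would discard 31-51% of placebo and 37-57% of lenalidomide follow-up time.

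**The case against.** **Redaction.** SAP 12.1 has a blacked-out block after the AE listings sentence, and text beside Protocol 16.7 is also blacked out. Exposure-adjusted tables could sit there. This stands: a reader might infer that the plan has no such analysis, but the documents support only that none is visible.

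**Tabulated, not tested.** Protocol 16.7 describes tables. The only inferential step is the optional exact test in SAP 12.1, and no AE hypothesis or decision rule hangs on it. This also stands, although the test, if used, would be applied to the crude counts.

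**Small effect.** At the documented cut the gap of 2.0 to 2.5 points is about 3 to 4 subjects of 160. The chance of a nominal p < 0.05 under equal rates would be about 8-10% instead of 5% (normal approximation). That is fair, and it limits the weight of the point.

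**The larger ratios.** A reader might take 1.40-1.89, or the 1.44 obtained with unlimited follow-up and no other reason to stop, as the size of the distortion. The documents do not support that. They show no date for Amendment 10 or 11, no count of subjects then on treatment and no toxicity-stopping rate. The SAP is also written for the double-blind stage with PFS co-primary, and at its first-step analysis both arms share one date.

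**Context already planned.** The plans include treatment duration by arm and time to first dose reduction or interruption (SAP 9), reasons for discontinuation (SAP 7), by-cycle presentation where applicable (SAP 6.4.1), follow-up AE tables (SAP 12.1), separate on-treatment and follow-up death tables (SAP 12.5), and assessment to progression after early stopping (SAP 5.1). These let a reader see that exposure is unequal. None of them puts AE incidence on equal time at risk.

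**Conclusion.** The point holds as a worthwhile reporting addition, not as an error in the plan. In the visible text, AE results by arm are crude once-per-subject percentages over windows that the design makes unequal. Under equal true rates, the planned medians and the assumed rate and accrual, the crude ratio at the 160-PFS-event cut is 1.16-1.20, about 2 percentage points.

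A reader might infer that the crude tables overstate lenalidomide's harm. The documents do not establish that: about 22% toxicity stopping on lenalidomide removes the gap, and about 36% reverses it. Larger ratios apply only to a later data cut and rest on assumed amendment dates. Confidence is medium, chiefly because of the redactions.

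**What to change.** Keep the crude tables. If the redacted text does not already do so, add to Protocol 16.7 and SAP 12.1, by arm, for key treatment-emergent AEs, SAEs and events of Grade 3 or higher:

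1. First events per 100 patient-years at risk.
2. Cumulative incidence of first event with death as a competing event, and a sensitivity analysis in which stopping treatment also competes. The choice of competing events is debatable, so both should be shown.
3. For any safety analysis after Amendment 10, treatment-window events with both arms cut at the Amendment 10 date, and later lenalidomide on-treatment events listed separately.
4. For SPMs, all study follow-up in both arms, without that cut.
5. A statement that any exact test on crude counts is read beside items 1 and 2.

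The cost is a few extra tables from data already collected. Two caveats should be written in. First, the patient-year rate assumes a constant hazard and dilutes early toxicity: in simulation, a hazard doubled on lenalidomide for the first 6 months only gives an overall rate ratio of 1.30-1.32 against 2.0 in those 6 months. That is why item 2 accompanies item 1. Second, censoring at the end of the window is informative if toxicity stops treatment, so the curves should be read with the reasons for discontinuation.

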## 2. SYNOPSIS

Name of Sponsor/Company: Celgene Corporation	
Name of Investigational Product: lenalidomide	
Protocol Number: CC-5013-CLL-002	
Protocol Title: A PHASE 3, MULTICENTER, RANDOMIZED, DOUBLE-BLIND, PLACEBO-CONTROLLED, PARALLEL-GROUP STUDY OF THE EFFICACY AND SAFETY OF LENALIDOMIDE (REVLIMID®) AS MAINTENANCE THERAPY FOR PATIENTS WITH B-CELL CHRONIC LYMPHOCYTIC LEUKEMIA FOLLOWING SECOND-LINE THERAPY	
Indication: Maintenance therapy in subjects with relapsed or refractory B-cell chronic lymphocytic leukemia (CLL) who have achieved at least partial response (PR) to second-line therapy.	

Study Duration: Subjects randomized to the lenalidomide treatment arm and on treatment at the time of Amendment #10 may, at the discretion of the investigator, continue on lenalidomide study treatment until disease progression (PD) develops. Subjects randomized to the placebo treatment arm and on treatment at the time of Amendment #10 will enter the survival follow-up period. Subjects who discontinue study treatment prematurely for reasons other than PD and subjects who develop PD (including disease transformation) will enter the survival follow-up period.
 
Subjects will be followed until all subjects in the study have been followed for at least 5 years from the last randomization, October 2020, (or have died/become lost to follow-up before the 5 years).
 
Amendment #11:
 
Subjects currently on lenalidomide treatment will discontinue lenalidomide treatment immediately and complete the Treatment Discontinuation assessment. The subjects will then transition to the survival follow-up period.
	
Phase of development: Phase 3

Objectives:
 
Primary:
 
 
To compare the efficacy of lenalidomide versus placebo maintenance therapy.
 
 
Secondary:
 
 
To evaluate the safety of lenalidomide versus placebo maintenance therapy.
 
	

Study Endpoints:
 
Primary
 
 
Overall Survival (OS)
 
	

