All subjects who receive at least 1 dose of study medication will be included in the safety analyses. AEs, clinical laboratory information, [REDACTED] will be tabulated and summarized. Subject incidence rates of all AEs (including serious, Grade 3, Grade 4, treatment-related [with and without discontinuation] and events requiring the discontinuation of investigational product), will be tabulated by system class, preferred term, and severity using Medical Dictionary for Regulatory Activities (MedDRA) terms and NCI CTCAE Version 3.0 severity grades with modifications. (Section 10.2.1). Time to first dose reduction will be summarized. The adverse event of infection will also be analyzed according to the grading system as recommended by the IWCLL guidelines for the diagnosis and treatment of CLL [REDACTED] (Appendix 22.4).

Death and clinically important AEs (including tumor flare, tumor lysis, second primary malignancies, and thrombosis) will also be summarized.

All other measurements will be summarized using means, standard deviations, medians, minimum, and maximum. Graphical displays will be provided where useful in the interpretation of results.

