### **10.3. Blinding**

This is now an open-label protocol. Therefore the dose of study drug will be identified on the package labeling (Amendment #10).

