### 12.3. Dosage Regimen

Subjects will be randomized (1:1) via IVRS to receive the following:

- Oral lenalidomide 2.5 mg capsule once daily on days 1-28 of the first 28 day cycle and if tolerated should be escalated starting with the second cycle to a 5 mg capsule once daily on days 1-28 of a 28 day cycle up to disease progression.

Following 5 continuous cycles at the 5 mg dose level, subjects who are tolerating the 5 mg dose level may be escalated to 10 mg once daily on days 1 through 28 of each 28-day cycle up to disease progression.

- Oral placebo capsule once daily every day for a 28 day cycle up to disease progression. The placebo treatment arm is discontinued in amendment #10.

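### Adverse-event and laboratory tables by regimen have no cut at Amendment #10, so open-label lenalidomide time with no concurrent placebo observation enters the placebo comparison

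*Protocol*

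**What the plan says.** **Analysis.** Protocol 16.7 states that "AE frequency will be tabulated by body system, MedDRA preferred term for each treatment regimen during the Treatment Phase" and that "In the by-subject analysis, a subject having the same event more than once will be counted only once". The safety paragraph of the protocol synopsis likewise promises "Subject incidence rates of all AEs". These are crude by-subject incidences. Treatment Phase is not defined, and no cut at Amendment #10 is stated. SAP 12.1 defines treatment-emergent events as running from first dose to "within 30 days after the last dose of the last study drug received" and allows an optional exact test between groups. SAP 12.2 and 12.3 summarize laboratory and vital-sign data over the treatment phase, also without a cut.

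**Conduct.** The synopsis says: "Subjects randomized to the placebo treatment arm and on treatment at the time of Amendment #10 will enter the survival follow-up period". Protocol 12.3 adds: "The placebo treatment arm is discontinued in amendment #10". Under the synopsis, lenalidomide subjects on treatment at that point may continue at the investigator's discretion; Amendment #11 later stops them. On blinding, Protocol 10.3 says: "This is now an open-label protocol".

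**Collection.** Table 2 schedules AEs at screening, Day 1, every 28 days and treatment discontinuation, with a dash under survival follow-up. Appendix 22.1 ends general AE recording 30 days after the treatment discontinuation visit. After that, section 8.1 collects only related serious AEs, plus second primary malignancies.

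**Purpose.** Protocol 6.2 makes safety of lenalidomide versus placebo the secondary objective, and 16.1 makes the comparison an aim of the statistical analysis.

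**The concern.** At Amendment #10 two things change together: which arm is observed for all AEs, and whether the people grading events and judging causality know the assignment. A table over the whole Treatment Phase takes its placebo column from blinded treatment plus a short tail. Its lenalidomide column adds a period that is unblinded and has no concurrent comparator.

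This bears on every count that grows with observation time: any AE, Grade 3 or higher, related events and worst laboratory grade. AEs leading to discontinuation are especially exposed, because a placebo subject whose treatment has already ended cannot contribute one. A reader of the final table could not separate drug effect from the change in who was observed and under what conditions.

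**Working it through.** There is no figure in the plan to reproduce. The check has two parts.

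**1. General AE collection by period**

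| Period | Placebo | Lenalidomide |
|---|---|---|
| Up to Amendment #10 | On treatment, blinded | On treatment, blinded |
| Amendment #10 to #11 | 30-day tail; then related AEs and serious AEs, second primary malignancies, deaths | 28-day visits on drug, assignment known |
| After Amendment #11 | As above | 30-day tail, then as placebo |

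The middle row is where the arms part. Hematology and chemistry follow the same 28-day pattern in Table 2. Vital signs do not: on treatment, after Day 1, they are scheduled only at discontinuation, so they are less affected. Nothing visible in Protocol 16.7 or SAP 12.1 to 12.3 separates the middle row from the first.

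**2. Illustration of the extra observation time**

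Inputs:
- Exponential time on treatment, with the design PFS medians of SAP 6.1 as a proxy: 20 months placebo, 32.3 months lenalidomide.
- Assumed: the same AE hazard λ = 0.01 per month in both arms, so no true drug effect.
- Assumed: Amendment #10 at month C after entry, the same for every subject, then L further open-label months. The 30-day tail is ignored.

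Stopping hazards: h = ln 2 / 20 = 0.03466 (placebo) and ln 2 / 32.3 = 0.02146 (lenalidomide).

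Crude incidence up to a cap: λ/(λ+h) × [1 − exp(−(λ+h) × cap)].

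With C = 24 and L = 12:
- Placebo, cap 24: 0.01/0.04466 × [1 − exp(−1.072)] = 0.2239 × 0.6576 = 14.7%
- Lenalidomide cut at Amendment #10, cap 24: 0.01/0.03146 × [1 − exp(−0.755)] = 0.3179 × 0.5300 = 16.8%
- Lenalidomide uncut, cap 36: 0.3179 × [1 − exp(−1.133)] = 0.3179 × 0.6778 = 21.5%

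Of the 6.8-point uncut gap, 21.5 − 16.8 = 4.7 points come from the open-label period. The other 16.8 − 14.7 = 2.1 points come from longer lenalidomide exposure under blinding.

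| C (months) | L (months) | Placebo % | Lenalidomide cut % | Lenalidomide uncut % | Added by open-label time | Gap left after cut |
|---|---|---|---|---|---|---|
| 12 | 12 | 9.3 | 10.0 | 16.8 | 6.8 | 0.7 |
| 24 | 6 | 14.7 | 16.8 | 19.4 | 2.6 | 2.1 |
| 24 | 12 | 14.7 | 16.8 | 21.5 | 4.7 | 2.1 |
| 24 | 24 | 14.7 | 16.8 | 24.8 | 8.0 | 2.1 |
| 36 | 12 | 17.9 | 21.5 | 24.8 | 3.3 | 3.6 |
| 60 | 12 | 20.9 | 27.0 | 28.5 | 1.5 | 6.1 |

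Over C = 12 to 60 and L = 6 to 24 months, open-label time is 4% to 58% of lenalidomide on-treatment time.

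**What exposure adjustment does here.** Expected time at risk to first event is [1 − exp(−(λ+h) × cap)]/(λ+h). Dividing incidence by it returns λ = 0.01 in all three cases: 0.147/14.7, 0.168/16.8 and 0.215/21.5 months. The illustrated differences are therefore wholly an observation-time effect.

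**The case against.** **Exposure-adjusted rates would be enough.** They remove everything the illustration measures, and that part of the objection stands. They do not separate blinded from unblinded reporting, and they supply no placebo data for the later period. The cut and the rates do different jobs, and at C = 60 the cut alone leaves 6.1 points of pure exposure difference.

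**The SAP predates the change.** It describes a double-blind trial with PFS and OS as co-primary endpoints and a working monitoring committee, so its treatment phase may have meant the blinded phase. That is fair to the SAP. However, its reference to the whole double-blind treatment period (section 9) governs exposure tables only, and the amended Protocol 16.7 was left without a cut.

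**The text is incomplete.** A block inside SAP 12.1 and the protocol sections on either side of 16.7 are redacted. The finding concerns the visible text, and pooling is inferred from the absence of any split.

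**Placebo collection does not stop.** A reader might infer from the dash in Table 2 that placebo AE data end altogether. The documents do not support that. The synopsis keeps related AEs and serious AEs under assessment after discontinuation, and section 8.1 keeps related serious AEs and second primary malignancies. SAP 12.1 also allows follow-up-phase tables when appropriate. What is lost is collection of all AEs regardless of relationship.

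**The error is conservative, and no formal test is required.** Protocol 16.7 is descriptive and the SAP exact test is optional. Extra observation time does overstate lenalidomide harm. But a comparative safety table should be interpretable, not merely biased in a known direction, and the reporting component has no known direction.

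**Conclusion.** The concern holds. Followed as written, the tables place open-label, one-arm lenalidomide experience into the crude comparison with placebo that serves the secondary objective. This should be settled before the comparative safety tables are produced.

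Extra observation can only raise crude lenalidomide incidence. Across the cases shown it adds 1.5 to 8.0 percentage points with no true difference. That range rests on assumed amendment timing, a common entry time, an assumed AE hazard and PFS medians standing in for time on treatment. It is not an estimate for this trial, and the true figure could be smaller or larger.

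Two stronger readings are tempting. One is that unblinded grading and causality calls bias the table against lenalidomide; nothing in the documents fixes that direction. The other is that a cut at Amendment #10 makes the comparison clean; the exposure difference under blinding remains, 14.7% against 16.8% in the month-24 case.

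**What to change.** Amend Protocol 16.7 and SAP 12.1 to 12.3 as follows:

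- Define the comparative safety window as the double-blind period: first dose to the earlier of last dose plus 30 days or the Amendment #10 unblinding or implementation date. Use the subject's own date if recorded, otherwise the site or study date; the documents do not show that a per-subject date exists.
- Use that window for all between-arm AE, laboratory and vital-sign comparisons.
- Show exposure-adjusted rates beside crude incidences.
- Report later open-label lenalidomide events in a separate single-arm table, with no placebo column and no between-arm test.
- Keep second primary malignancies and deaths on full follow-up in both arms.

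The cost is wording and one extra set of safety tables. The downside is that late lenalidomide events appear outside the comparative table, so the report should point readers to the single-arm one.
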